ICD-10-CM	International Classification of Diseases, Tenth Revision, Clinical Modification
IP	Inpatient
IRR	Incidence Risk Ratio
ITP	Immune Thrombocytopenia
MDS	Minimum Data Set
MRR	Medical Record Review
NDC	National Drug Codes
NHS	Non-hemorrhagic Stroke
OP-ED	Outpatient Emergency Department
OP/PB	Outpatient and Professional
PE	Pulmonary Embolism
PHI	Protected Health Information
PII	Personal Identifying Information
PMaxSPRT	Poisson Maximized Sequential Probability Ratio Test

POS	Place of Service
PPV	Positive Predictive Value
RCA	Rapid Cycle Analysis
RR	Risk Ratio
SCCS	Self-Controlled Case Series
SCRI	Self-Controlled Risk Interval
SE	Standard Error
SSD	Shared Systems Data
STEMI	ST-elevation Myocardial Infarction
VAERS	Vaccine Adverse Events Reporting System

Protocol Synopsis / Executive Summary

Background

As of June 30, 2021, three coronavirus disease 2019 (COVID-19) vaccines (BNT162b2, Pfizer-BioNTech; mRNA-1273, Moderna; and Ad26.COV2.S, Johnson & Johnson/Janssen) have been granted emergency use authorization (EUA) by the United States (US) Food and Drug Administration (FDA). The FDA Center for Biologics Evaluation and Research (CBER), in partnership with the Centers for Medicare & Medicaid Services (CMS), conducted surveillance of these three vaccines using the Medicare database, which includes patients who were 65 years of age and older. The surveillance activity used the rapid cycle analysis (RCA) method also known as the near real-time surveillance. The RCA detected a statistical association between the Pfizer-BioNTech COVID-19 vaccine and four adverse events of special interest (AESI). As the next step, the CBER Biologics Effectiveness and Safety (BEST) program has developed this protocol to conduct an in-depth epidemiological study to evaluate the signals detected in the RCA study. This study will evaluate the potential association between the Pfizer-BioNTech COVID-19 vaccine and the four AESI that signaled in the RCA including acute myocardial infarction (AMI), pulmonary embolism (PE), disseminated intravascular coagulation (DIC), and immune thrombocytopenia (ITP). The study will also evaluate the Moderna and Janssen COVID-19 vaccines and the four AESI using the same methods. It should be noted that the RCA is a surveillance method and produces a crude measure of association between an exposure and an outcome. In the COVID-19 vaccines RCA, the crude relative risk reflected the comparison of the observed rate of AESI following COVID-19 vaccination with the historical incidence rates prior to the authorization of COVID-19 vaccines. Although the RCA adjusted for nursing home residency status, age, sex, and race, it did not adjust for other potential confounding by other factors. The current study aims to conduct a self-controlled design that will better adjust for confounding.

Objective

The primary objective of this study is to evaluate the risk of AMI, PE, DIC, and ITP following vaccination with Pfizer-BioNTech, Moderna, and Janssen COVID-19 vaccine using a self-controlled case series (SCCS) design.

Data Source

This study will use the CMS Medicare administrative claims data for elderly persons aged 65 years and older in the US.

Exposure and Outcomes

The exposure is defined as any dose of each of the three Pfizer-BioNTech, Moderna, and Johnson & Johnson/Janssen COVID-19 vaccines, as identified in the medical plan of interest by appropriate product codes. The outcomes include incident AMI, PE, DIC, and ITP identified by the International Classification of Diseases, Tenth Revision, Clinical Modification (ICD10-CM) codes.

Methods

This study will use the SCCS design with post-vaccination control interval as the primary analysis. As the secondary analysis, the study will use control intervals defined within the observation period, including both pre- and post-vaccination time periods. As the exploratory analysis, the study will use the self-

controlled risk interval (SCRI) design with a pre-vaccination control interval only. A sample of charts for each AESI will be obtained and adjudicated for case confirmation. Quantitative bias analyses will be considered to evaluate the robustness of the risk estimates.

1 Background/ Introduction

COVID-19 is a contagious respiratory illness caused by the SARS-CoV-2 virus. Three COVID-19 vaccines (BNT162b2, Pfizer-BioNTech; mRNA-1273, Moderna; and Johnson & Johnson/Janssen, Ad26.COV2.S) are available in the US under an EUA granted by the FDA. CBER is monitoring the safety of these vaccines through both passive and active surveillance methods.¹ The passive surveillance relies on reporting of adverse events and deaths by manufacturers, health care providers, patients, and others using the Vaccine Adverse Events Reporting System (VAERS), and the active surveillance uses the BEST Initiative infrastructure along with collaboration with CMS. The active surveillance utilizes health care data from tens of millions of individuals along with different study designs and statistical methods.

The RCA study evaluated the risk of 14 AESI after exposure to one of the three COVID-19 vaccines. The evidence for the selection of these AESI originated from serious events that have followed other vaccinations, that are potentially related to novel platforms or adjuvants, that are related to COVID-19 severity and may potentially relate to vaccine failure/immunogenicity (enhanced disease), or events that are potentially specific to particular populations of interest. These AESI are not known to be associated with COVID-19 vaccines based on available pre-authorization or pre-licensure evidence.²

The RCA study was conducted in the Medicare Shared Systems database including patients aged 65 years and older at the time of COVID-19 vaccination. No statistical signals were identified for the Moderna or Janssen vaccines nor for 10 of 14 AESI after vaccination. The RCA detected statistical signals for four AESI, including pulmonary embolism (PE), acute myocardial infarction (AMI), disseminated intravascular coagulation (DIC), and immune thrombocytopenia (ITP), following receipt of any dose of the Pfizer-BioNTech vaccine (manuscript in preparation). As of June 25, 2021 (data through June 12, 2021), the observed number of deep vein thrombosis (DVT) and non-hemorrhagic stroke (NHS) events following Pfizer-BioNTech and Moderna vaccination exceeded the pre-specified number of expected events; The RCA completed for DVT and NHS with no evidence of a statistically significant increase in the risk. No other AESI have reached the pre-specified statistical threshold at this time, but the monitoring for the rest of the events continues.

Given the limitations of the RCA study design, this study plans to further evaluate the statistical association of the four aforementioned AESI with all three authorized vaccines.

2 Study Objectives

The primary objective of this study is to evaluate the risk of AMI, PE, DIC, and ITP following vaccination with Pfizer-BioNTech, Moderna, and Janssen COVID-19 vaccine using a self-controlled case series (SCCS) design.

2.1 Primary Analysis

Evaluate the risk of AMI, PE, DIC, and ITP after exposure to each COVID-19 vaccine using the self-controlled case series (SCCS) design. The primary analysis compares the risk of each event in a time

interval after vaccination (risk window) to that in time intervals post-vaccination after completion of the risk window (control window) within the study period.

2.2 Secondary Analysis

Evaluate the risk of AMI, PE, DIC, and ITP after exposure to each COVID-19 vaccine using the self-controlled case series (SCCS) design. The secondary analysis compares the risk of each event in a time interval after vaccination (risk window) to that in time intervals other than the risk window within the observation period, including both pre- and post-vaccination time (control window).

2.3 Exploratory Analysis

Evaluate the risk of AMI, PE, DIC, and ITP after exposure to each COVID-19 vaccine using the self-controlled risk interval (SCRI) design. The exploratory analysis compares the risk of each event in a time interval after vaccination (risk window) to that in a time interval pre-vaccination (control window).

3 Data Sources

The data source for this study is the US Medicare claims and enrollment databases in the CMS Medicare Shared Systems Data (SSD). Medicare provides health insurance coverage to approximately 61 million persons aged ≥ 65 years in the US as well as nearly 9 million persons aged < 65 years with end-stage kidney disease (ESRD) or with certain disabilities in 2018.³ Only persons who were 65 years of age or older at the time of COVID-19 vaccination are included in the analysis. Demographics and information on death is derived from the enrollment databases. Information on vaccinations, health covariates, preventive services, and outcomes are derived from Medicare Part A (inpatient) and Part B (outpatient and community settings) and Part D (prescription) claims. Medicare claims data undergo three stages of processing: enumeration, adjudication, and final payment. CMS Medicare SSD, which consists of claims sourced after enumeration, will be used in this study. SSD is updated daily and is over 80% complete within 30-70 days depending on the care setting and outcome. Personal identifying information (PII) and protected health information (PHI) is also available in Medicare data, enabling the possibility of conducting medical record reviews (MRR) to validate AESI using these data. However, FDA does not have access to PII or PHI, and it only receives aggregate results without any PII or PHI attached. Information on nursing home residency status is derived from clinical assessment of residents in the Minimum Data Set (MDS). In addition, health-seeking attitudes and frailty conditions from the Medicare Current Beneficiary Survey may be considered for confounding adjustment. For each person in the study, administrative claims from all care settings will be linked to create a longitudinal record of their health encounters, diagnoses, and drug prescriptions.

4 Exposure and Outcomes

4.1 Care Settings

Identification of exposures and AESI will occur within specific care settings of interest. Table 1 summarizes how the inpatient (IP), outpatient emergency department (OP-ED), and outpatient and professional (OP/PB) settings used in this study are defined.

Table 1. Care setting definitions

Care Setting	Definition
Inpatient (IP)	Hospital inpatient acute facility claims (e.g., UB-04 with type of bill = 11x)
Outpatient Emergency Department (OP-ED)	Outpatient facility claims (e.g., UB-04) in ED
Outpatient & Professional (OP/PB)¹	Outpatient facility claims (UB-04) -OR- Professional claims (CMS-1500) that contain at least one non-lab place of service ²

¹ Including all sources of professional claims (e.g., urgent care etc.)

² Independent laboratory place of service code = 81

The IP setting is defined by hospital inpatient acute facility claims. Hospital inpatient facility claims encompass the entire episode of inpatient care, and generally have more accurate diagnosis coding compared to professional claims given that diagnosis coding is linked to payment for facility claims. Additionally, if medical record requests are initiated, facilities are more responsive to those requests.

The OP-ED setting is defined using outpatient facility claims with services provided in the Emergency Department (ED), as defined by place of service (POS) and revenue codes. The OP-ED setting is a subset of the OP/PB setting.

The OP/PB setting, which includes both ED and non-ED services, is defined by all outpatient facility claims and all professional claims with non-laboratory places of service. This setting captures the broad spectrum of outpatient care regardless of care setting and provider type. Claims with laboratory places of service will be excluded since they often include “rule-out diagnoses” that may not represent true current or underlying conditions.

4.2 Exposure (COVID-19 Vaccination)

Exposure is defined as the receipt of any dose of Pfizer-BioNTech, Moderna, and Johnson & Johnson/Janssen COVID-19 vaccine, as identified within the medical plan of interest by appropriate product codes such as Current Procedural Terminology (CPT®)/Healthcare Common Procedure Coding System (HCPCS) codes or National Drug Codes (NDCs) in any care setting (Table 2). The list of valid codes will be reviewed periodically and updated if new codes are added. Patients with a claim containing a relevant code or codes will be classified as vaccinated. In the CMS Medicare claims data, COVID-19 vaccination has been primarily billed through Part B using CPT/HCPCS codes.

If an individual has more than one vaccination code for the same brand and dose occurring on the same day, the codes will be de-duplicated so that the individual contributes only one exposure for that brand’s dose to the study. If an individual has codes representing multiple doses (e.g., 1st dose and 2nd dose) of the same brand on the same day, only the code representing the earliest administration will be kept (e.g., first dose). If no administration code is observed for an individual, and thus dose order is unknown, then dose number assignment will be based on the presence of prior doses of the same brand. If multiple brands are observed on the same day, that person will be excluded from the study. Dose spacing patterns for two-dose COVID-19 vaccines will be investigated in the data and a standard minimum time gap between doses may be instituted. In this situation, if sequential doses for the same brand are observed in close proximity

(e.g., within a few days of each other), the study may exclude the subsequent dose. Additional vaccination pattern investigation will be conducted to determine how to group or de-duplicate observed vaccination doses for a single dose vaccine (e.g., Janssen COVID-19 Vaccine).

Table 2. Healthcare Common Procedure Coding System (HCPCS)/ Current Procedural Terminology (CPT) and National Drug Codes (NDC) for COVID-19 vaccines as of June 15, 2021

HCPCS/CPT Code	Manufacturer	Name	Vaccine Administration Code	NDC 10/NDC 11 Labeler Product ID (Vial)	Dosing Interval
91300	Pfizer	Pfizer-BioNTech COVID-19 Vaccine	0001A (1 st dose) 0002A (2 nd dose)	59267-1000-01 59267-1000-02 59267-1000-03	21 Days
91301	Moderna	Moderna COVID-19 Vaccine	0011A (1 st dose) 0012A (2 nd dose)	80777-0273-10 80777-0273-99 80777-0273-15 80777-0273-98	28 Days
91303	Janssen Biotech Inc.	Janssen COVID-19 Vaccine	0031A	59676-0580-05 59676-0580-15	N/A

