5.4.1 Primary Analysis: SCCS with Post-vaccination Control Intervals

The observation period will start from the vaccination date (day 0) of the first dose, if there are two doses, and extend to day 90. The post-vaccination control interval is defined as all follow-up time during the observation period following either the first or second COVID-19 vaccine dose (for two-dose COVID-19 vaccines) that is outside of the risk interval(s) until day 90 post-vaccination, end of study period, disenrollment, or death, whichever occurs first; while likely uncommon, this includes any time between the end of the first dose risk window and the receipt of a second dose. Figure 1 presents some hypothetical examples in design. Individuals who only accrued data during the risk intervals will be ineligible to be included in the analysis (Section 5.5.1).

Figure 1. Hypothetical examples of SCCS design with post-vaccination control intervals for one-dose and two-dose vaccines

[figure not shown]

Note: The hypothetical risk interval following one dose is up to 28 days. However, the length of the risk and control intervals will vary for each AESI.

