5.5.1 Primary Analysis: SCCS with Post-vaccination Control Intervals

Eligible vaccinees should meet the following inclusion/exclusion criteria.

Inclusion criteria:

- (i) Medicare beneficiaries enrolled in Part A (hospital insurance) and Part B (medical insurance) during the study observation period, as well as during the clean window prior to the occurrence of the AESI.
 - Continuous enrollment will be required from the start of an AESI's clean window relative to the occurrence of the AESI through day 90 post-vaccination, the end of the study period, disenrollment, or death, whichever comes first.
- (ii) Received at least one dose of a COVID-19 vaccine during the vaccination period of interest. The end of the vaccination period is defined as the vaccination cut-off date.
 - The vaccination cut-off date will be selected for each outcome to reduce the possibility of bias due to incomplete capture of events.
- (iii) For case population only, had a record of the AESI diagnosis during the study observation period.

Exclusion criteria:

- (i) Less than 65 years of age at the start of observation period.
- (ii) Does not contribute follow-up time to both risk and control intervals. If individuals disenroll, or reach the end of the study period during the risk window prior to accumulating any time for post-vaccination control intervals, they will be excluded.
- (iii) Had COVID-19 vaccination patterns that do not conform to expectations for the analysis of interest, e.g., doses that occur within a short time period following another dose or have a higher than expected dose number; more specific rules will be determined once more data on vaccination patterns are available.
- (iv) Had a diagnosis of the AESI during the AESI-specific clean window (Table 3) or during alternate clean windows assessed in sensitivity analyses.
- (v) Received different COVID-19 vaccines for the first and second dose. Based on the preliminary assessment, such a scenario only occurred in approximately 0.12% of cases with an AESI.

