5.7.2 Primary Analysis: SCCS with Post-vaccination Control Intervals

For the primary self-controlled analysis, the risk of the AESI following any dose will be evaluated, without distinguishing between dose numbers. This analysis will compare the AESI rates in the risk and control intervals using a conditional Poisson regression model. For two-dose COVID-19 vaccines, the model assumes constant risk throughout each risk window, regardless of how close together the two doses may be administered (i.e., no additive risk from overlapping risk windows). Sensitivity analysis (Section 5.7.2.1) is planned to evaluate the robustness of this assumption. Under the assumption of constant risk, the following model will be fit:

$$\log(E(Y|X)) = \beta_1(\text{risk_interval}) + \log(t) + \text{strata}(\text{patient_id})$$

Y = AESI
risk_interval = binary term indicating AESI occurrence in risk interval
t = interval
patient_id = term identifying the patient

Under this model, the null and alternative hypotheses can be written as:

$$H_0: e^{\beta_1} = 1 \quad H_a: e^{\beta_1} \neq 1$$

where e^{β_1} will be interpreted as the rate ratio for the AESI in the risk interval compared to the control intervals. Thus, statistical significance of the coefficient on the risk interval variable at a pre-specified level will indicate a statistically significant association between COVID-19 vaccination and the AESI. Statistical significance will be determined using 95% confidence intervals of rate ratios and two-sided p-values ($p \leq 0.05$).

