To evaluate the assumption of constant risk throughout each risk interval for two-dose COVID-19 vaccines, potential differences in risk will be stratified by vaccine dose if sample size permits. Analyses will be restricted to vaccinations where the administration codes are concordant with the order of vaccination procedure codes. The overall risk interval will be categorized as 1) dose 1 only; 2) overlapping dose 1 and dose 2, where risk intervals of each dose overlap; and 3) dose 2 only. Risk of the AESI occurring in these three categories of the risk intervals will be compared separately with the post-vaccination control intervals. Figure 4 presents some hypothetical examples in SCCS design with varying risk during the risk intervals and post-vaccination control intervals.

Figure 4. Hypothetical examples of SCCS design with varying risk during the risk interval and post-vaccination control intervals for two-dose vaccines

Note: The hypothetical risk interval following one dose is up to 28 days. However, the length of the risk and control intervals will vary for each AESI.

To assess the robustness of the case definition:

- Different clean window lengths will be explored.
 - Instead of using a fixed clean window length to define “incident AESI”, the study may consider clean windows that are longer than the length of the pre-defined clean windows (Table 3), constructed retrospectively from the anchoring date using all available data, for AMI, PE, DIC,

and ITP; however, extending the continuous enrollment to cover the full period of all available data is not required.

- In addition, a clean window shorter than the pre-defined clean window may be examined for AMI and PE as shown in Table 4 below.

Table 4. Alternative clean windows

AESI	Care Setting	Clean Window
Acute Myocardial Infarction (AMI)	IP	28 days ¹⁹
Pulmonary Embolism (PE)	IP, OP/ PB	183 days ²⁰

- To exclude chronic ITP among cases, all thrombocytopenia events in the pre-specified clean window (Table 3) will be excluded. Chronic ITP may be more common in the older adult population.²¹
- Alternative event definitions in Table 5 will be considered. Restriction to the inpatient setting is likely to increase the likelihood to capture acute events or relapse/exacerbation of the chronic events.

Table 5. Alternative AESI definitions

AESI	Care Setting
Acute Myocardial Infarction (AMI)	IP, primary diagnosis position
Type I AMI	IP
Type I AMI	IP, primary diagnosis position
Pulmonary Embolism (PE)	IP

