5.7.4 Exploratory Analysis: SCRI with a Pre-vaccination Control Interval

The study will compare the rate of AESI in the risk intervals after the first dose and all doses combined with those in the pre-vaccination control interval in a conditional Poisson regression that estimates incidence rate ratio (IRR).

When sample size permits, subgroup analyses by age group, sex, race/ethnicity, and nursing home residency status will be performed.

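### The same-day code rule in section 4.2 ignores dose history, so some true second doses are numbered as first doses and fail the concordance restriction in 5.7.2.1, which leaves the days after them unassigned

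*Protocol*

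**What the plan says.** Section 4.2 has two separate rules for dose number.

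- Several dose numbers of one brand coded on one day: "only the code representing the earliest administration will be kept (e.g., first dose". No exception is made for a person who already has an earlier dose of that brand on record.
- No administration code at all: "then dose number assignment will be based on the presence of prior doses of the same brand". This is the only place where dose history decides the number.

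The dose number is then used unevenly across the analyses.

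- The primary analysis (5.7.2) does not use it: "the risk of the AESI following any dose will be evaluated, without distinguishing between dose numbers".
- The sensitivity analysis in 5.7.2.1 that tests the constant-risk assumption does: "potential differences in risk will be stratified by vaccine dose if sample size permits". It carries a further condition: "Analyses will be restricted to vaccinations where the administration codes are concordant with the order of vaccination procedure codes".
- The exploratory SCRI (5.7.4) looks at the "risk intervals after the first dose and all doses combined".

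Section 5.4.1 defines control time as follow-up after either dose "that is outside of the risk interval(s) until day 90 post-vaccination". Exclusion (iii) in 5.5.1 removes people who "Had COVID-19 vaccination patterns that do not conform to expectations for the analysis of interest", with the specific rules left for later.

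**The concern.** Take a person with 0001A on day 0, then 0001A and 0002A both billed on day 21. The history shows that the day-21 vaccination is the second dose, and one of the two codes says so. The same-day rule discards that code and keeps the first-dose code. The record now shows two first doses and no second dose. The day-21 vaccination is second in order but carries a first-dose code, so it fails the concordance condition in 5.7.2.1. The protocol has itself created the discordance, since a correct code was in the claims.

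At stake is the dose-stratified analysis, which is the planned check on the constant-risk assumption of the primary model. It loses true second doses. If the days after a dropped dose were also treated as unexposed, its comparator would contain exposed time.

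**Working it through.** **Which doses are affected.** Three things must coincide: an earlier dose of the brand is recorded, both dose codes appear on the later date, and they are the same brand. If no earlier dose is recorded, keeping the first-dose code agrees with the observed order and nothing goes wrong.

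**What happens to the days.** The 5.7.2.1 restriction is worded for vaccinations, not persons, and does not mention person-time. Exclusion (iii) in 5.5.1 might remove the person, but its examples are doses too close together and a dose number higher than expected; two first-dose codes at the usual spacing match neither. The 5.7.2.1 analysis for under-captured second doses is defined for people with one observed dose, whereas these people have two. The point is therefore open. What follows applies only if the person is kept and the days fall into control time.

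**Inputs.**
- Dosing interval: 21 days (Pfizer-BioNTech), 28 days (Moderna), Table 2.
- Risk window: days 1-28 (AMI, PE, DIC), days 1-42 (ITP), Table 3.
- Observation to day 90, section 5.4.1.
- RR: AMI 1.42, DIC 1.91, ITP 1.44, Table 6. These are any-dose Pfizer-BioNTech figures, and section 5.8 assumes similar values for the other brands.
- Share of two-dose cases affected, f: not in the protocol. Assumed range 0.1% to 10%.

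The protocol gives no figure of its own on this point to reproduce.

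**Day counts per affected person (days 1-90).** C is the correct number of control days; m is the number of post-dose-2 risk days that would be added to it.

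| Brand, window | Post-dose-2 days outside the dose-1 window | m | C | Counted as control (C + m) |
|---|---|---|---|---|
| Pfizer-BioNTech, 28 | 29-49 | 21 | 41 | 62 |
| Moderna, 28 | 29-56 | 28 | 34 | 62 |
| Pfizer-BioNTech, ITP 42 | 43-63 | 21 | 27 | 48 |
| Moderna, ITP 42 | 43-70 | 28 | 20 | 48 |

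Days on which the two windows overlap would also be labelled dose 1 only: 7 and 0 days in the first two rows, 21 and 14 in the last two.

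**Dose-1 ratio among affected persons.** Assuming one true RR in every risk category, apparent RR = RR / [(C + m × RR) / (C + m)].

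- Pfizer-BioNTech AMI: 1.42 / [(41 + 21 × 1.42) / 62] = 1.42 / 1.142 = 1.24
- Moderna, same RR: 1.42 / [(34 + 28 × 1.42) / 62] = 1.42 / 1.190 = 1.19
- Pfizer-BioNTech ITP: 1.44 / [(27 + 21 × 1.44) / 48] = 1.44 / 1.1925 = 1.21
- Moderna ITP: 1.44 / [(20 + 28 × 1.44) / 48] = 1.44 / 1.257 = 1.15

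**Whole analysis at an assumed share f.** Pooling person-time, apparent RR = RR × (C + f × m) / (C + f × m × RR). This approximates what the conditional fit would give.

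| f | Pfizer-BioNTech AMI (1.42) | Moderna DIC (1.91) |
|---|---|---|
| 0.1% | 1.420 | 1.909 |
| 1% | 1.417 | 1.896 |
| 5% | 1.405 | 1.844 |
| 10% | 1.392 | 1.786 |

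For example, at 10%: 1.42 × 43.1 / 43.982 = 1.392. Moderna DIC shows the largest dilution of the brand and event pairs examined.

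**Which ratio moves.** The model in 5.7.2 is stratified by patient. Once dose 2 is dropped, an affected person has only dose-1 risk time and control time, and so informs only the dose-1 coefficient.

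**Primary analysis.** Only a code is discarded. The vaccination and its date remain, the any-dose risk interval opens on the right day, and no day changes category.

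**The case against.** The strongest reply is that the protocol nowhere sends the days after a dropped dose into control time. Section 5.4.1 defines control time by the risk intervals after either dose and makes no reference to code agreement, so those days can be read as staying out of it. Exclusion (iii) could remove the whole person, and detailed code cleaning can be left to a later document. This stands as far as control time goes: contamination is one possible implementation, not the stated plan. It does not answer the numbering problem. Section 4.2 does not leave same-day conflicts open; it fixes a rule, and that rule gives the wrong number whenever an earlier dose is on record.

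A reader might also infer more than the text supports:

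- That every dose-specific ratio is pulled toward 1. Affected persons contribute nothing to the overlap or dose-2 ratios; those ratios lose data but are not directly diluted by them.
- That the main result is biased. The primary analysis ignores dose number and does not change.
- That 1.24 or 1.19 is the expected study result. Those values describe affected persons only, and the share is unknown.
- That the first-dose SCRI is wrong. A relabelled dose could enter it as a first dose, but only if doses are picked by code and not by order, which 5.7.4 does not say.

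**Conclusion.** A minor point that holds in a limited form. The same-day rule in 4.2 misnumbers a true second dose when an earlier same-brand dose is recorded and both codes fall on the later date. That vaccination then fails the restriction in 5.7.2.1, provided concordance is judged after the 4.2 cleaning. The effect is confined to a sensitivity analysis that runs only if numbers allow.

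Dilution of the dose-1 ratio is conditional on the person being kept and the days being counted as control, which the protocol neither states nor rules out. Under that reading, with equal true RR across doses and the Table 2 spacing, the loss is sizeable among affected persons. Across the analysis it is slight at small shares: in the third decimal at 1% for Pfizer-BioNTech AMI, and about 0.03 at 10% (1.42 to 1.392). The protocol gives no frequency, so the overall size cannot be settled from it.

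**What to change.** In section 4.2, when same-day dose codes of one brand conflict, assign the dose number from prior same-brand doses: second dose if an earlier dose is recorded, otherwise first. This extends to conflicting codes the logic already used when no administration code exists.

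In section 5.7.2.1, state what happens after a discordant dose. Either exclude persons with any discordant dose from the dose-stratified analysis, or keep them but remove the Table 3 window after that dose, so that it never counts as control time. Reporting the number of such persons by brand would show whether the matter is of any size.

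The cost is two sentences and a small change in code, using variables already built. A few cases or days leave one sensitivity analysis; the primary analysis is untouched.
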